**12 STATEMENTS OF COMPLIANCE**

The clinical investigation will be conducted according to the principles of the Declaration of Helsinki and other guidelines, regulations and Acts.

The clinical investigation shall not begin until the required approval/favorable opinion from ICBE and the IRB have been obtained. Any additional requirements imposed by ICBE and the IRB shall be followed.

**Compensation for injury**

General liability insurance is arranged by Royal Philips.

Title: Clinical Investigation Plan		Author: [name]		Company Restricted	
DocID: ICBE-2-28674	Version: 2.0	Date: 2019-02-18	Status: Approved	Page: 29 of 35	
IRBMANAGER PILOT – QI PROJECT					

Sponsor wishes to obtain dispensation from statutory obligation to provide insurance, because participating in the study is without risks. A reasoned request will be made to accredited EC and this dispensation will be mentioned here.

**13 INFORMED CONSENT PROCESS**

*Select all that apply:*

- The requirement for informed consent has been waived (i.e., not required by law OR waived by IRB/REC/METC). Upload waiver if available.
- Written informed consent will be obtained from adult participants
- Assent will be obtained from children/minors
- Parental permission will be obtained when children are participating
- Surrogate consent will be obtained when participants lack decisional capacity
- Deferred consent will be obtained [e.g., emergency research]
- Click-through consent will be obtained [Internet/app-based research]
- Implied consent [i.e., consent through action such as taking a test]

13.1 Consent Process (See Section 13.3 re Assent & Permission)  
 Study participation is voluntary. Potential subjects, are given the most current ICBE/IRB approved consent form to read. They will be provided ample time (+1 week) for review and an opportunity to ask questions about the study. The informed consent form will be provided by the CRO during the recruitment process. If they agree to participate, the CRO will schedule the participant for participation and they will sign the consent form before the start of the study. They will be given a copy of the signed document for their records. Each of these actions/steps will be documented. Only after Informed Consent has been obtained, may the remaining study procedures begin.

13.2 New Information about the Study  
 Any new information about the study that may affect a consented subject’s decision to be in the study (e.g., changed procedures, safety, etc.), will be communicated in a timely manner. Depending on the nature of the new information, subjects who have completed the study may or may not be informed, documenting the decision and justification as well as any activities for informing completed subjects. Additionally, the approving IRB will also be informed. The currently approved Consent Form will be updated and submitted to the ICBE and approving IRB for review and approval. Active subjects will be re-consented, following the above process, with the newly-approved consent form.

13.3 Inability to Provide Consent (children or adults)  
 N/A

**14 ADVERSE EVENTS AND DEVICE DEFICIENCIES**

**Definitions**

Title: Clinical Investigation Plan		Author: [name]		Company Restricted	
DocID: ICBE-2-28674	Version: 2.0	Date: 2019-02-18	Status: Approved	Page: 30 of 35	
IRBMANAGER PILOT – QI PROJECT					

Adverse events and adverse device effects, device deficiencies and serious adverse events and serious adverse effects and, unanticipated serious adverse device effects are defined in the table below:

Definition	Description
Adverse Event (AE)	Any untoward medical occurrence, unintended disease or injury, or untoward clinical signs (including abnormal laboratory findings) in subjects, users or other persons, whether or not related to the investigational medical device  NOTE 1 This definition includes events related to the investigational medical device or the comparator.  NOTE 2 This definition includes events related to the procedures involved.  NOTE 3 For users or other persons, this definition is restricted to events related to investigational medical devices.
Adverse Device Effect (ADE)	Adverse event related to the use of an investigational medical device  NOTE 1 This definition includes events related to the investigational medical device or the comparator.  NOTE 2 This definition includes events related to the procedures involved.  NOTE 3 For users or other persons, this definition is restricted to events related to investigational medical devices.
Serious Adverse Event (SAE)	Adverse event that a) led to death, b) led to serious deterioration in the health of the subject, that either resulted in 1) a life-threatening illness or injury, or 2) a permanent impairment of a body structure or a body function, or 3) in-patient or prolonged hospitalization, or 4) medical or surgical intervention to prevent life-threatening illness or injury or permanent impairment to a body structure or a body function, c) led to foetal distress, foetal death or a congenital abnormality or birth defect  NOTE Planned hospitalization for a pre-existing condition, or a procedure required by the CIP, without serious deterioration in health, is not considered a serious adverse event.
Serious Adverse Device Effect (SADE)	Adverse device effect that has resulted in any of the consequences characteristic of a serious adverse event or that might have led to any of these consequences if suitable action had not been taken or intervention had not been made or if circumstances had been less
Unanticipated Adverse Device Effect (UADE)	Serious adverse device effect which by its nature, incidence, severity or outcome has not been identified in the current version of the risk analysis report  NOTE Anticipated serious adverse device effect (ASADE) is an effect which by its nature, incidence, severity or outcome has been identified in the risk analysis report.

**Reportability**

All adverse events shall be reported to the Study Manager. ADEs, SAEs, SADEs and USADEs shall be reported to the Q&R office as well. The Director Q&R shall assess the ADEs, SAEs, SADEs and USADEs for reportability to Competent Authorities.

**Reporting process**

Reporting shall include the date of the adverse event, research subject ID#, description of the adverse event, treatment, resolution, and assessment of both the seriousness and the relationship to the investigational device and study procedures.

Title: Clinical Investigation Plan		Author: [name]		Company Restricted	
DocID: ICBE-2-28674	Version: 2.0	Date: 2019-02-18	Status: Approved	Page: 31 of 35	
IRBMANAGER PILOT – QI PROJECT					

**Timelines**

The time period in which the principal investigator shall report all adverse events and device deficiencies to the sponsor and, where appropriate, to ECs and the regulatory authority, and the details of the process for reporting device deficiencies, are detailed in the table below.

Category	Report to Study Manager	Report to Accredited Ethics Committee	Report to Q&R office
	by Principal Investigator	by Principal Investigator	by Principal Investigator by Study Manager
Adverse Event (AE)	Periodic reporting to Sponsor Periodic collection by Sponsor	As part of Sponsor’s Clinical Investigation Report	
Adverse Device Effect (ADE)	Immediate, < 24 hr	As part of Ethics Committee Reporting timelines or < 24 hr following instructions by Sponsor	Immediate, <24 hr
Serious Adverse Event (SAE)		As part of Ethics Committee Reporting timelines or < 24 hr following instructions by Sponsor	
Serious Adverse Device Effect (SADE)		Immediate, < 48 hrs	
Unanticipated Adverse Device Effect (UADE)		As part of Ethics Committee Reporting timelines or < 24 hr following instructions by Sponsor	

**Foreseeable adverse events and anticipated adverse device effects**

No adverse events and anticipated adverse device effects are foreseen. The only event we foresee is fatigue of participants that are participating in our study.

Since there are no possible adverse events, there is no foreseen need to contact the IRB .

Device malfunction will be reported to the sponsor directly who then needs to take a decision to stop/suspend or continue the trial depending the software fault and the risks of achieving the trial objectives. There is no risk for the subjects even if the device is at fault.

**Emergency contact details**

N/A

**Information regarding the Data Management Committee, if established**

N/A

**Incidental Finding Reporting**

An Incidental Finding is a finding concerning an individual research participant that has potential health or reproductive importance and is discovered in the course of conducting research but is beyond the aims of the study.

All incidental findings will be documented in a timely manner throughout the study. The report Incidental Finding Report Form (see ICBE SP) will be in the receipt of Philips Research Q&R Office within 7 business days of when the researcher first learns about the finding.

Title: Clinical Investigation Plan		Author: [name]		Company Restricted	
DocID: ICBE-2-28674	Version: 2.0	Date: 2019-02-18	Status: Approved	Page: 32 of 35	
IRBMANAGER PILOT – QI PROJECT					

## 15 INVESTIGATOR BROCHURE (IB)

An IB is needed and included in the ICBE study dossier.

## 16 VULNERABLE POPULATION

According to ISO 14155, a vulnerable subject is an individual whose willingness to volunteer in a clinical study could be unduly influenced by the expectation, whether justified or not, of benefits associated with participation or of retaliatory response from senior members of a hierarchy in case of refusal to participate.

None—this study uses live human participants but not from vulnerable populations

*Indicate whether you will include any of the following (vulnerable) populations in your study:*

- Children or viable neonate (birth to age 28 days)
- Cognitively impaired
- Pregnant women (except USA)
- Fetuses
- Neonates of uncertain viability or nonviable
- Prisoners
- Poor/uninsured
- Educationally disadvantaged (limited education, e.g., high school drop out)
- Students (including interns, residents, fellows)
- Minorities (includes migrants, refugees)
- Elderly (over age 65 years)
- Terminally ill
- Other (check box and specifically discuss below)

*Informed consent form will be provided with detailed information about the study.  
Psychometrists who are experienced with this age group will collect the data.*

## 17 SUSPENSION OR PREMATURE TERMINATION

In case the study is ended prematurely, the investigator will notify the IRB and the ICBE about the reasons for the premature termination.

Title: Clinical Investigation Plan		Author: [name]		Company Restricted	
DocID: ICBE-2-28674	Version: 2.0	Date: 2019-02-18	Status: Approved	Page: 33 of 35	
IRBMANAGER PILOT – QI PROJECT					

The principal investigator or authorized designee shall inform the subjects of the reasons for resumption.

The following criteria and arrangements for suspension or premature termination of the whole clinical investigation or of the clinical investigation in one or more investigation sites apply:

- Philips decides to stop the study.

In case of suspension or premature termination of the clinical investigation, the following requirements apply for subject follow-up.

- N/A

## 18 PUBLICATION POLICY

Results of clinical investigation may be submitted for publication. Philips shall register and report the results of this applicable trial on [clinicaltrials.gov](http://clinicaltrials.gov).

50-54	50	25	25	33	7	7	3	5	15	30
55-59	50	25	25	35	6	6	3	5	16	29
60-64	50	25	25	36	6	5	3	5	16	29
65-69	50	25	25	37	5	5	3	5	15	30
70-74	50	25	25	37	6	5	2	6	15	29
75-80	50	25	25	40	4	4	2	9	18	23

Variance Matrix		Age Variance	Male	female	Sex Variance	White	White Variance	Black	Black Variance	Hispanic	Hispanic Variance	Other	Other Variance	< 12 years	< 12 Variance	12 years	12 Variance	> 12 years	> 12 Variance
50-54	50	1	25	25	±2	33	-1	7	±1	7	±1	3	at least 2	5	exact	15	±1	29	±2
55-59	50	1	25	25	±2	35	-1	6	±1	6	±1	3	at least 2	5	exact	16	±1	29	±2
60-64	50	1	25	25	±2	36	-1	6	±1	5	±1	3	at least 2	5	exact	16	±1	29	±2
65-69	50	1	25	25	±3	37	-1	5	±1	5	±1	3	at least 2	5	exact	15	±1	30	±2
70-74	50	1	25	25	±3	37	-1	6	±1	5	±1	2	at least 1	6	exact	15	±1	29	±2
75-80	50	1	25	25	±3	40	-1	4	±1	4	±1	2	at least 1	9	exact	18	±1	23	±1
total	250	250	at least 115	No more than 135	±10	185	up to -5	27	at least 25	25	at least 22	13	at least 8	30	at least 30	80	at least 75	140	at least 130

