### 2.2 Intended purpose

The IntelliSpace Cognition tool is intended to be used as an adjunctive tool in the assessment of an adults' level of cognitive functioning.

The IntelliSpace Cognition tool provides health care professionals with an overview of both the overall cognitive performance as well as specific cognitive domains

The IntelliSpace Cognition tool provides health care professionals with a method to compare a person's cognitive performance over different assessments (moments in time).

The results from IntelliSpace Cognition tool are intended to be used by healthcare professionals who have participated in IntelliSpace Cognition trainings.

The data collected by IntelliSpace Cognition are intended to be collected under the supervision of a HCP

The IntelliSpace Cognition tool is not intended as a stand-alone or adjunctive diagnostic device.

The assessments provided via the IntelliSpace Cognition tool may be used for a wide variety of patient groups, as well as healthy individuals when a HCP wishes to gain more insight into cognitive performance.

Disclaimer:

- The cognitive model of IntelliSpace Cognition tool has been scientifically validated for assessing the cognition of healthy people in the age group of 55-80
- The IntelliSpace Cognition tool has not been validated for use with adults under the age of 55 or over the age of 80 and doesn't include normative data for adults under the age of 50 or over the age of 80.

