### Primary hypotheses

The following primary hypotheses will be tested in the study:

Aim 1.

- A. Digital and paper-pencil normed test scores are comparable. We consider the two versions of a test comparable when the digital normed score is on average within .3 sd of the paper normed score and the two normed scores correlate at least .6.
- B. Test-retest reliability of the digital tests is comparable to test-retest reliability of the paper-pencil tests. We consider the reliability to be comparable when we observe no significant difference in a z-test between the digital and the paper-pencil test-retest correlations.

Title: Clinical Investigation Plan		Author: [name]		Company Restricted	
DocID: ICBE-2-28674	Version: 2.0	Date: 2019-02-18	Status: Approved	Page: 20 of 35	
IRBMANAGER PILOT – QI PROJECT					

C. Construct validity of the digital tests is comparable to the construct validity of the paper-pencil tests. We consider construct validity to be comparable when confirmatory factor analysis yields the same factor structure for digital and paper-pencil tests.

Aim 2.

D. The score(s) provided by the ROCFT and Clock Drawing Test scoring algorithms on ISC are correlated highly (> .8) to the score provided by manual scoring for the same drawings.

Aims 3 & 4 have no accompanying hypotheses.

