## 7 STATISTICAL CONSIDERATIONS

**Statistical design, analyses and power considerations**

Below we describe the planned analyses for each aim and hypothesis. The tests are scored by two raters (with 30% overlap) and inter-rater agreement is assessed prior to proceeding with the following analyses. All correlations mentioned below are Pearson correlations. Retest correlations are corrected for the variability of the normative sample (Allen & Yen, 2002; Magnusson, 1967). Correlation between paper and pencil measures are corrected for measurement error (Padilla & Veprinsky, 2012). In our power analyses we assume an alpha of .05.

Title: Clinical Investigation Plan		Author: [name]		Company Restricted	
DocID: ICBE-2-28674	Version: 2.0	Date: 2019-02-18	Status: Approved	Page: 25 of 35	
IRBMANAGER PILOT – QI PROJECT					

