**Aim 1 comparison of psychometrics.**

Hypothesis A: Digital and paper-pencil test scores are comparable.

For each test, we will first compute age-only referenced scores for digital and paper-pencil version separately. Referenced scores are computed based on the regression based norms (procedure described below under aim 3) and are represented as z-scores indicating a participant's deviation from what would be expected based on the norm sample for a participant with identical demographic characteristics. We then compute the correlation between digital and paper-pencil referenced scores within participants in group A and B (which are the groups in which participants completed both digital and paper-pencil versions of the tests), which needs to be  $r > .6$  to be considered comparable. Our planned sample size allows us to detect a correlation of  $r > .2$  with 80% power. We also perform an equivalence test for each test, comparing the distribution of digital normed scores with paper-pencil normed scores, using a two-one-sided-t-test approach (TOST; Schuirmann, 1987), with equivalence bounds of  $\pm .3$  sd, which we have 99% power to detect. Our planned sample size would allow us to detect equivalence with bounds of at least  $\pm .21$  with 80% power.

Hypothesis B: Test-retest reliability is comparable.

Test-retest reliability will be tested by examining for each test the correlation between the digital tests in phase 1 and phase 2 (group C) and comparing this to the correlation between the paper-pencil tests in phase 1 and phase 2 (group D). High test-retest correlations are expected ( $r > 0.7$ ), except for the ROCFT copy condition, since the scores of this condition generally show a moderate ceiling effect. The planned sample size for group C and group D each yield 80% power to detect  $r > .37$ .

Hypothesis C: Construct validity is comparable.

Construct validity will be investigated by means of two confirmatory factor analyses (CFA), one for each group (digital vs. paper-pencil). We expect to see that the factor structure that fits the paper-pencil data (phase 1, group B & D) well, will also fit the digital data (phase 1, group A & C) well. Assuming that at most two variables per test are included in the CFA, the subject-to-variable ratio is near 10:1 for each CFA.

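### Hypothesis A tests one pooled mean of separately age-normed scores, so it cannot show whether the digital-paper difference depends on age

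*Combined protocol and SAP*

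**What the plan says.** Section 5 (Primary hypotheses, Aim 1 A) sets the rule for each test: "the digital normed score is on average within .3 sd of the paper normed score and the two normed scores correlate at least .6". Section 7 (Aim 1, Hypothesis A) turns the mean part into a two-one-sided-tests (TOST) analysis: "We also perform an equivalence test for each test, comparing the distribution of digital normed scores with paper-pencil normed scores", with bounds of ±0.3 SD. The same paragraph says that age-only referenced scores are first computed for the digital and paper versions separately, from the regression norms described under Aim 3. Aim 3 describes a norm group for digital data only (groups A and C in phase 1, plus group E). No paper norm group is named.

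Age enters through quotas, minimization and norming. Section 7 has no age term, age stratum or age-specific criterion for Hypothesis A.

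Three other places give age its weight. Section 2.2 says that the cognitive model "has been scientifically validated for assessing the cognition of healthy people in the age group of 55-80". Section 3 treats digital-paper comparability as essential to the validity of the digital tests and of that model. The sampling-plan table at the end of the document sets equal targets by age band; its last row reads "75-80 50 25 25 40 4 4 2 9 18 23". Claim 3 in section 5, that digital tests have psychometrics similar to paper, rests on Aim 1.

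**The concern.** Stylus-and-tablet testing is a setting in which a format effect could plausibly depend on age. An overall mean near zero does not exclude a difference beyond 0.3 SD at one or both ends of the 55-80 range.

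Norming each format on its own age regression goes further. It takes out the part of the format difference that changes linearly with age before the comparison is made. An age breakdown of those same normed scores would then show little, however large the underlying drift.

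What is at stake is claim 3. As planned, the study could support similarity on average but would be silent on whether it holds at 57 or at 78, although the data to answer that are collected anyway.

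**Working it through.** **Inputs.** Groups A and B have 100 + 100 = 200 pairs (section 6.1). The margin is ±0.3 SD. On alpha: "In our power analyses we assume an alpha of .05", applied to each one-sided test.

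**The plan's own figures.** The plan states for the ±0.3 bounds "sd, which we have 99% power to detect", and adds "Our planned sample size would allow us to detect equivalence with bounds of at least" ±0.21 at 80% power. With a paired TOST, a true difference of 0 and an SD of the difference of 1:
- Power = 2Φ(0.3√200 − 1.645) − 1 = 2Φ(2.598) − 1 = 0.991.
- Bound at 80% power = (1.645 + 1.282)/√200 = 0.207.

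Both figures reproduce, so SD 1 of the paired difference is the planning unit. It corresponds to a correlation r of 0.5, since SD = √(2(1 − r)). At r = 0.6 the SD is 0.894, and at r = 0.8 it is 0.632.

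**Who is in the analysis.** The five bands from 55 to 80 sum to 5 × 50 = 250. That is the size of the digital norm group (100 + 50 + 100), not of A+B. If A+B is spread evenly (assumption), it has 200/5 = 40 people per band.

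**Both formats on one common scale.** For a true overall mean m with SE = 1/√200 = 0.0707, P(pass) = Φ((0.3 − m)/SE − 1.645) + Φ((0.3 + m)/SE − 1.645) − 1. For deficits rising linearly from 0 in the youngest band:
- To 0.3 SD (m = 0.15): 68%, or 96% at r = 0.8.
- To 0.4 SD (m = 0.20): 41%, or 72%.
- To 0.5 SD (m = 0.25): 17%, or 30%.
- To 0.8 SD (m = 0.40): about 0.

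A second set of drifts was simulated with 10,000 runs, ages uniform on 55-80, and difference d0 + g(age − 67.5)/12.5 plus N(0,1) noise:
- d0 = 0, g = 0.45 (+0.38 at 78, −0.36 at 57.5): passes 99%.
- d0 = 0.05, g = 0.40 (0.39 at 78): 96%.
- d0 = 0.10, g = 0.30 (0.35 at 78): 87%.
- d0 = 0.15, g = 0.20 (0.32 at 78): 67%.

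**Separate norms against a common norm.** This simulation covers groups A-E with 1,500 runs. It assumes r = 0.7, a decline of 0.03 SD per year and a phase 2 practice gain of 0.2 SD. The digital norm comes from A, C and E. The paper norm comes from B and D in phase 1, an assumption because the plan names none. Each cell gives the size of the mean normed difference left in 75-80, then the TOST pass rate. The common-norm ranges cover scoring both formats on the digital or on the paper norm.

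| Assumed digital deficit | Own norm per format | One common norm |
|---|---|---|
| Linear, 0 to 0.4 SD | 0.00; 94% | 0.38; 52-54% |
| Linear, 0 to 0.5 SD | 0.00; 94.5% | 0.49; 21-22% |
| Linear, 0 to 0.8 SD | 0.00; 96% | 0.78; 0% |
| 0.6 SD in 75-80 only | 0.18; 96% | 0.52-0.53; 92-93% |
| Advantage 0.4 to deficit 0.4 | 0.00; 94% | 0.38; 100% |

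The correlation criterion was met in 92-98% of runs under either norming, so it does not catch the drift.

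**What the existing data can show.** A ±0.3 TOST within one band of 40 has power 2Φ(0.3√40 − 1.645) − 1 = 0.20 at SD 1. A regression on all 200 pairs does better. With ages uniform on 55-80 the age variance is 25²/12 = 52.08, and the SE of the fitted difference at age x is √((1 + (x − 67.5)²/52.08)/200):
- At 78: √(3.117/200) = 0.125, a 95% half-width of 0.245 SD.
- At 57.5: √(2.92/200) = 0.121, a half-width of 0.237 SD.

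The slope test has 80% power for a change of 0.56 SD from the first to the last band at SD 1, or 0.35 SD at r = 0.8.

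**The case against.** The case for leaving the plan alone has several sound parts.
- Section 5 defines comparability as an average, and claim 3 names no age range.
- The 55-80 statement in section 2.2 is about the cognitive model, not about digital-paper equality at each age.
- The product reports age-referenced scores (section 3), and the norms are built from digital data. A linear age-related format effect would largely be absorbed there.
- No drift size comes from the documents.
- On a common scale, a deficit that starts at zero and grows large often fails already. The 99% pass rate needs a crossover, with the difference running in opposite directions at the two ends.

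All of this stands and limits the point. A reader might infer that any digital disadvantage growing with age would be passed as comparable, or that the oldest users would receive wrong scores. The documents support neither. On a common scale the result depends on the overall mean, and the consequence falls mainly on claim 3 rather than on the age-normed score. A reader might also take the 75-80 row as the Hypothesis A sample; it belongs to a 250-person table.

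The objection does not remove the gap itself. Section 7 plans no estimate of how the format difference changes with age, and section 3 makes the validity of the tests and of the model depend on comparability.

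**Conclusion.** The point holds in a limited form. Hypothesis A gives one pooled verdict per test on scores normed separately by format, and it cannot show whether the digital-paper difference depends on age. If each format has its own age regression, as section 7 reads, linear deficits reaching 0.4 to 0.8 SD leave about nothing in the oldest band and pass in 94-96% of simulated runs. If both formats share one norm, a drift averaging 0.05 to 0.15 SD and exceeding 0.3 SD at 78 passes 67-96% of the time at the planning SD, while one averaging 0.25 SD mostly fails.

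These figures rest on assumed drifts, an even age spread in A+B, an SD of the difference between 0.632 and 1, and an assumed paper norm group. They show what the plan could miss, not that a drift exists.

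**What to change.** In section 7, Hypothesis A, keep the overall TOST. For each test, pre-specify a regression on age of the A+B paired difference (digital minus paper), using raw scores or both formats scored on one common norm. The common scale is essential, because the same regression on separately normed scores would hide a linear drift. State which group supplies any paper norm.

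Report the age slope and the fitted difference at about 57.5 and 78, each with a confidence interval, in the SD unit of the margin and read against 0.3 SD. Where the margin is exceeded, qualify the age range of claim 3.

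Do not add a pass/fail gate on the point estimates at the two ages. A drift inside the margin (mean 0, g = 0.20, so 0.20 × 10.5/12.5 = 0.17 SD at 78) would fall from a 99% to about a 78% chance of passing, and a point estimate does not demonstrate equivalence. Do not add band-wise TOSTs either, given about 20% power per band at SD 1.

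The cost is one regression per test on data already collected, plus some wording. Precision at the age ends is limited (about ±0.24 SD at SD 1), and the claim may become narrower.
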